- Presence or sequelae of gastrointestinal, liver, kidney, or other conditions known to interfere with absorption, distribution, metabolism, or excretion of drugs,
- Recent blood or blood product donation.

C. Study Design and Research Methods

Up to 68 subjects will undergo two 10-hour frequent blood sampling studies on consecutive days. However, the PI will first need to identify the dose level that results in a significant pharmacodynamic (PD) effect, namely an increase in serum inhibin B, with a target PD response rate of 80% across patients. Therefore, up to 9 subjects will also be needed for a pilot portion of the study (up to 3 subjects at each level will be needed to identify the level at which the target response rate is reached).

The total maximum number of subjects consented will be 120.

At the date of this protocol (10/11/2016), 6 subjects had already been treated in the pilot portion of this protocol.

- 3 subjects were treated at 10 IU; none of them showed an increase in inhibin B; adverse events of delayed menses and hot flushes thought be related to GnRH antagonist use were reported.
- 3 subjects were treated at 20 IU; none of them showed an increase in inhibin B; adverse events of delayed menses and hot flushes thought be related to GnRH antagonist use were reported.

With this version of the protocol (10/11/2016), we propose to treat 9 subjects with 30 IU, administered every 60 minutes over 10 hours, for a total of 300 IU.

Preliminary analysis of the completed study visits thus far (09/3/2019) have indicated the obese cohort has lower serum FSH levels than the normal weight cohort in response to the addition of rFSH on Day 2. We want to investigate if the difference we see is because FSH is being excreted in urine. We propose to collect urine at 4 nonspecific time points during day 1 to obtain a baseline value of FSH in urine for each participant and at the following specific time points T=0, 30, 60, 120, 240, 480, 600 minutes during day 2. We understand that asking the participants to provide 3 urine samples in the first hour of day 2 might not be possible for every participant. Therefore, we will ask each participant to give at least 2 samples (0 and 60 min on day 2) and request the 30-minute sample be tried but not required.

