Subjects will also be provided a second Alpco EasySampler® Stool Collection Kit and be asked to return an optional stool sample within 7 days of the study visit.

All subjects who received 30 IU of the rFSH will have safety follow up phone calls the next day, 3-5 days and 7-10 calendar days after discharge from the clinic. Any adverse events identified during that call will be reported and followed until resolution.

Patient confidentiality. Patient confidentiality will be respected and guarded by adhering to HIPAA guidelines for personal health information. We will describe this approach to study subjects both verbally and in the informed consent document. They will be told that their information will be made available to appropriate representatives of the National Institutes of Health who may be reviewing the records in accordance with accepted policies and procedures. This approach has been successfully utilized by us previously for numerous clinical research studies at our institution, including the studies directed or co-directed by the PI. No breaches of patient confidentiality or inappropriate disclosure of their medical information have transpired. All participants will be given a study number that will identify their file. Files will be kept in the Clinical and Translational Research Center, under lock and key, or in the PI or research coordinator's office. Identifying information other than the study number will be redacted from participant's study records such that the file cannot be linked to the participant by name. The code linking study numbers to name will be kept by the research coordinator in a separate folder in a separate locked cabinet in a locked office. No identifying information will be released in the course of publication or presentation of study findings.

Samples will be sent to the University of Virginia to run the inhibin B assay as UVA has one of the most sensitive and precise assays for inhibin B. No identifiers will accompany the samples when sent to UVA.

E. Data Analysis Plan:

- 1) To test whether the difference in maximal inhibin B and E2 response between day 1 and day 2 depends on group (obese vs. normal weight) we will use a two-sample t-test.
- 2) In a second phase of analysis, we will adjust for potential confounders such as age and AMH level. We will repeat this analysis on the other secondary outcome measures.

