- 3) To understand how inhibin B and E2 respond to FSH stimulation after GnRH antagonist we will compare groups in relation to the maximal change in inhibin B.
- 4) To understand how changes in inhibin B relate to changes in estradiol, linear regression will be used to assess whether the maximal change in inhibin B between day 1 and day 2 is statistically associated with the change in maximal E2 response between day 1 and day 2 (i.e. $\Delta MaxE2 = \beta_0 + \beta_1 \Delta Inhibin B$).
- 5) To characterize the changes in the microbiome we will analyze bacterial diversity by 16s ribosomal RNA sequencing. We have extensive experience in the analysis of the human microbiome in the environment, nares, vaginal, and intestinal tract and will analyze our data as previously described.²⁰⁻²² Microbiome data will be used for exploratory analyses in relation to clinical and other parameters measured among the study participants.

Pilot:

We are planning to assess the change in inhibin B levels following repeated bolus dosing of recombinant FSH (rFHS) following GnRH antagonist blockade. For the purposes of this study, we are interested in identifying the dose level that results in a significant pharmacodynamic (PD) effect, namely an increase in serum inhibin B, with a target PD response rate of 80% across patients. Statistical significance for the PD response at the patient level will be identified as an increase of 2.3 times the baseline standard deviation for inhibin B measurement in normal women. Using the data provided in the above table, showing a standard deviation in serum inhibin B concentration in normal women of 36.3 pg/mL, an increase in serum inhibin B of 83.5 pg/mL following FSH dosing would be considered a significant PD effect. This value provides a one-sided statistical significance at the 0.05 significance level, appropriate as there is an *a priori* anticipation that the response will occur in only one direction.¹⁶ To determine statistical significance of the dose level of 10 IU IV every 60 minutes, three study subjects will

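### The regression of E2 change on inhibin B change (Data Analysis Plan, item 4) has no group term, so its slope can mix the obese versus normal-weight contrast with the association inside each group.

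*Combined protocol and SAP*

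**What the plan says.** Section IV.E, item 4, gives its aim as "To understand how changes in inhibin B relate to changes in estradiol". Taking the change in peak E2 as the outcome, it states that "linear regression will be used to assess whether the maximal change in inhibin B between day 1 and day 2 is statistically associated". The model follows in full: change in maximal E2 equals an intercept plus one coefficient times the change in inhibin B. It has no group indicator and no interaction, and nothing says that it is fitted within each group.

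Three other places bear on this:

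- Item 1 sets out "To test whether the difference in maximal inhibin B and E2 response between day 1 and day 2 depends on group (obese vs. normal weight"), using a two-sample t-test. A group difference in both changes is therefore the trial's main question.
- Item 2 says "we will adjust for potential confounders such as age and AMH level" and extends that analysis to the other secondary outcomes. It comes before item 4, concerns the group comparison, and does not put group into the regression.
- Section IV.C reports from interim data that "the obese cohort has lower serum FSH levels than the normal weight cohort in response to the addition of rFSH on Day 2". It also gives the sample size: "Up to 68 subjects will undergo two 10-hour frequent blood sampling studies on consecutive days". The split between groups is not stated.

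**The concern.** The pooled sample is a mixture of two groups recruited from non-adjacent BMI ranges (18.5 to 24.9, and above 30.0 kg/m²). When both variables in a regression have different means in two groups, a single line through all the points is pulled towards the line joining the two group means. The slope can then be non-zero although the hormones are unrelated within either group, or it can overstate or understate a real relation.

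The trial's hypothesis is that ovarian steroid and protein output are both lower in obesity, so the scenario that disturbs item 4 is the one the study was designed to find. The interim FSH observation makes a shared difference plausible, because FSH is the stimulus given to raise both hormones. It does not show that the two changes differ by group.

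At stake is the interpretation of item 4. From the pooled slope alone, a reader could not tell whether women with a larger inhibin B change also have a larger E2 change, or whether both changes are simply smaller in one BMI group.

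**Working it through.** The plan attaches no sample size, power or significance level to item 4, so there is no planned figure to reproduce. The check is algebra followed by simulation.

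**Inputs from the documents.** The item 4 model; two BMI groups; up to 68 women.

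**Assumptions.** 34 per group (20 per group as a variant); two-sided 0.05; normal errors; unit within-group SD for both changes. Let dx and dy be the group differences in inhibin B change and E2 change, in within-group SDs, and let b be the within-group slope.

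**A rough scale for d.** The preliminary table gives baseline inhibin B as 96.6 (36.3) in 10 normal-weight women and 67.7 (38.2) in 11 obese women. If the brackets are SDs, as the pilot section treats the 36.3, the pooled SD is √[(9 × 36.3² + 10 × 38.2²)/19] = 37.3. The difference is then 28.9/37.3 = 0.77 SD. This is a baseline level, not a change, and the table has no E2 row, so it only indicates the order of size.

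**Formula.** With equal groups, the group difference adds dx²/4 to the variance of inhibin B change and dx·dy/4 to the covariance:

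pooled slope = (b + dx·dy/4) / (1 + dx²/4)

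**Case 1: no within-group association (b = 0), dx = dy = d.** At d = 0.8 the slope is 0.16/1.16 = 0.14. At d = 1.0 it is 0.25/1.25 = 0.20. Rejection rates come from 40,000 simulated trials per setting.

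| d | Pooled slope | Rejection, 34 per group | Rejection, 20 per group |
|---|---|---|---|
| 0.3 | 0.02 | 5.4% | 5.2% |
| 0.5 | 0.06 | 7.8% | 6.5% |
| 0.7 | 0.11 | 14.6% | 10.5% |
| 0.8 | 0.14 | 20.4% | 13.9% |
| 1.0 | 0.20 | 38.3% | 24.0% |
| 1.5 | 0.36 | 89.4% | 67.3% |

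With a group term the rate is 4.9% to 5.2% in every row. A separate run of 20,000 trials per setting at 34 per group gave 7.3%, 20.5%, 38.8% and 89.4% for d = 0.5, 0.8, 1.0 and 1.5.

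**Case 2: only one hormone differs by group (b = 0, d = 1.0).** Pooled rejection is 5.0% and 5.2% for the two hormones in turn. Both changes must differ for a spurious association to appear.

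**Case 3: a real within-group slope, b = 0.35, 34 per group.**

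- dx = 0.8, dy = 0.28: (0.35 + 0.056)/1.16 = 0.35, no bias. Here the E2 difference is what the inhibin B difference predicts (0.35 × 0.8 = 0.28).
- dx = dy = 0.3: (0.35 + 0.0225)/1.0225 = 0.36.
- dx = dy = 0.5: (0.35 + 0.0625)/1.0625 = 0.39.
- dx = dy = 0.8: (0.35 + 0.16)/1.16 = 0.44.
- dx = 0.8, dy = −0.8: (0.35 − 0.16)/1.16 = 0.16, with power 26% against 84% with a group term.

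**The case against.** The strongest reply is about the estimand. Item 4 asks whether the two changes are statistically associated and does not say within group. If both differ by group, the association across all women is real and rejecting its null is no error. That is correct: the rates in Case 1 are errors only against a within-group null. But item 4 states an explanatory aim, and a pooled slope cannot separate the hormones moving together from both being lower in one group. At the least, the plan must say which slope it means.

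Second, if FSH exposure drives both hormones, it probably creates some association inside each group too, so zero association may be the least natural case. With b = 0.35, same-direction differences of 0.3 to 0.5 SD move the slope only to 0.36 to 0.39. This stands, and it is why the size is given as a range that includes harmless cases.

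Third, nothing in the documents supports group differences in opposite directions, and differences of 1.0 to 1.5 SD have no source. Both points stand. Those rows show how the model behaves and are not forecasts.

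Fourth, the results of items 1 and 3 will show readers whether the groups differ. They would flag the problem but would not give the within-group slope.

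Finally, a group term removes the difference in group means only. It does not remove variation in FSH exposure among women of the same group, so the adjusted slope is still an association and not proof of ovarian coupling. That limit stands.

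**Conclusion.** The concern holds. The item 4 model is written out without group, and nothing elsewhere in the plan adds it. If both changes differ by group, the slope is a mixture, except in the special case where the E2 difference is exactly what the within-group slope predicts from the inhibin B difference.

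The consequence is conditional. It is negligible for shared differences of about 0.3 SD or when one hormone alone differs, and material from about 0.7 to 0.8 SD, where a within-group null is rejected in roughly 15% to 20% of trials instead of 5%. These rates assume 34 per group, two-sided 0.05, normal errors and no within-group association. The documents supply none of the group differences needed to narrow the range.

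The model should be changed, but the primary comparison is not threatened: item 4 is supporting, and the group t-tests in item 1 do not depend on it.

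**What to change.** Rewrite the item 4 model as: change in maximal E2 = b0 + b1 × (change in inhibin B) + b2 × group. Report b1 with its confidence interval as the common within-group slope. Examine the group-by-inhibin B interaction as a check on whether the slopes differ, and state that its power is low. The slope without group may be shown beside it, labelled as the marginal association across all women.

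The cost is one added term: error degrees of freedom fall from 66 to 65 if 68 women are analysed. No new data are needed and study conduct does not change. In the case where the pooled slope is unbiased (b = 0.35, differences of 0.8 and 0.28 SD), adding group lowers power from about 89% to 84%. Writing the model into the plan now also avoids choosing between the two slopes after seeing the results.

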Appendix: Study Visits and Procedures Flow Chart

SAFETY Follow Up phone calls (24 hours, 3-5 days and 7-10 post-discharge)

** All blood draws conducted by CTRC Inpatient or Outpatient staff
